**Multicenter double-blind placebo-controlled parallel group
randomized clinical trial of efficacy and safety of MMH-407 in the
treatment of acute respiratory viral infection**

Phase III

Sponsor	ООО «NPF «MATERIA MEDICA HOLDING»
Protocol number	MMH-407-001
Version date:	July 01, 2019
ClinicalTrials.gov Id:	NCT04244084

Protocol Summary

This document represents the protocol summary for the study on human patients. The study will be carried out in accordance with ICH GCP, National Standard of the Russian Federation GOST 52379-2005 "Good Clinical Practice", Helsinki Declaration of World Medical Association, relevant requirements of the regulatory authorities as well as the study procedures.

Title of Study

Multicenter double-blind placebo-controlled parallel group randomized clinical trial of efficacy and safety of MMH-407 in the treatment of acute respiratory viral infection.

Phase: III

Sponsor: OOO "NPF "MATERIA MEDICA HOLDING", Moscow, Russia

Protocol No. MMH-407-001

Objective of the study

- To evaluate the efficacy and safety of MMH-407 in the treatment of acute respiratory viral infection (ARVI).

Endpoints

Primary endpoint

1. Time to resolution of ARVI symptoms^{1,2} (PCR-confirmed).

Secondary endpoints

1. Severity of ARVI (clinically diagnosed and/or PCR-confirmed); based on the area under the curve (AUC) data for the Total Severity (TS) score³ on days 1-6 of the observation).
2. Percentage of patients with resolution of ARVI symptoms (clinically diagnosed and/or PCR-confirmed).
3. Time to resolution of ARVI symptoms (clinically diagnosed and/or PCR-confirmed).
4. Percentage of patients with resolution of ARVI symptoms (PCR-confirmed).
5. Dosing frequency of antipyretics on days 1-3 of therapy⁴.
6. Percentage of patients requiring administration of antibiotics or hospitalization on 4-14 days of the observation.

¹ Time from enrollment to symptom resolution. **Resolution of ARVI symptoms** is defined if body temperature $\leq 37.30^{\circ}\text{C}$ within 24 hours (without further increase during observation period) + absence/presence of ARVI symptoms ≤ 2 .

² Based on a patient diary.

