³ **Total Disease Index** will be calculated based on the intensity of each ARVI symptom (body temperature, systemic symptoms and nasal/pharyngeal/chest symptoms in points) with further statistical processing of data by OOO "NPF "Matera Medica Holding" experts. To determine total score, absolute values of body temperature measured in Celsius degrees will be converted into relative units (or points) based on the following classification: $\leq 37.3^{\circ}\text{C}=0$; $37.4-38.0^{\circ}\text{C}=1$; $38.1-39.0^{\circ}\text{C}=2$; $\geq 39.1^{\circ}\text{C}=3$.

⁴ Based on a patient diary.

Safety assessment

- Adverse events (AEs) during the therapy, AEs severity and relation to the study drug, and AEs outcomes.
- Changes in vital signs during the treatment.
- Percentage of patients with clinically relevant laboratory abnormalities.

Study design

Study design: multicenter, double blind, placebo-controlled, parallel group randomized clinical trial.

The study will enroll outpatients of either gender aged 18-70 years old with clinical manifestations of ARVI within the first day after the onset of the disease during seasonal ARVI morbidity.

After signing patient information sheet and informed consent form, medical history, thermometry, objective examination, laboratory tests and concomitant medication will be performed. Severity of ARVI symptoms is evaluated with 4-point scale.

The nasopharyngeal swabs for PCR diagnosis and verification of respiratory viruses will be performed prior to therapy to confirm the viral etiology of ARVI.

If a patient meets all inclusion criteria and does not have any exclusion criteria, at Visit 1 (Day 1) he/she will be randomized into one of two groups: the 1st group will take MMH-407 according to the dosage regimen for 5 days; the 2nd group will take Placebo according to MMH-407 dosage regimen for 5 days.

The study will use electronic patient diary for recording morning and evening axillary body temperature (measured using a mercury-free Geratherm Classic thermometer) and disease symptoms (Symptom Severity Score). Besides, antipyretic dosing (if applicable) and any aggravation in a patient's condition (if applicable, for safety evaluation/AE documentation) will also be recorded in a patient diary. The investigator will provide instructions on filling the diary; at Visit 1 the patient together with a doctor will record ARVI symptom severity and body temperature in the diary.

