Overall the patient will be monitored for 14 days (screening, randomization - up to 1 day, study treatment period – 5 days, follow-up period – up to 2 days; delayed "phone" visit – day 14).

Symptomatic (Standard) treatment

Throughout the study, the patients may receive symptomatic ARVI therapy:

- antipyretic/non-steroidal anti-inflammatory drug (paracetamol/ibuprofen)

and/or

- vasoconstrictive nasal drug – oxymetazoline/naphazoline

and/or

- cough suppressant/expectorant drug – butamirate/ambroxol, bromhexine, guaifenesine, acetylcysteine.

Indications for prescription of antipyretics:

Increased body temperature $> 39^{\circ}\text{C}$ in patients without complications and co-morbidities and $> 38^{\circ}\text{C}$ in patients with co-morbidities (congestive heart failure, hepatic, renal diseases; history of convulsive syndrome).

If antipyretic was taken by the patient on his own (without doctor recommendation) with no indications the patient is not excluded from the study. The patient should record the values of thermometry before taking the drug, its name and dose.

Not considered as prohibited products:

- systemic antihistamines (R06A)
- medication for the treatment of obstructive airway diseases (R03).

Prohibited concomitant therapy

Two weeks before inclusion in the study*, as well as during the study (from signing of the information sheet for patient /informed consent form and initiation of screening) the following medication are not allowed (their ATC group is indicated in brackets):

[figure not shown]
1. Antivirals (J05).
2. Antimicrobials and antiseptics for local treatment of oral diseases (A01AB).
3. Medications for the treatment of throat diseases (R02A).
4. Immunostimulants (L03), including:
 - interferon inducers (acridonoacetic acid, meglumine acridone acetate/cycloferon®, umifenovir/arbidol®, kagocel®, tilorone/amixin®, polyadenyl acid + polyuridylic acid/poludan®, sodium oxodihydroacridinyl acetate/neovir®, lavomax®, tilaxin®, etc.)
 - interferons;

- bacterial immunomodulators (including ribomunyl®, sodium ribonucleate/ridostin, etc., sodium deoxyribonucleate/derinat®, etc., IRS-19, imudon®, broncho-munal®, etc.).
- pidotimod/immunorix;
- interleukins;
- synthetic immunostimulants (levamisole, alpha-glutamyl-tryptophan/thymogen, etc.);
- medication with thymus hormones.

5. Non-steroidal anti-inflammatory drugs (M01, except for ibuprofen).
6. Analgesics and antipyretics (N02A, N02B except for paracetamol).

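### Does the primary endpoint need a rule for temperatures taken around antipyretic doses, and a sensitivity analysis to match?

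*Combined protocol and SAP*

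**What the plan says.** The primary endpoint is time to resolution of symptoms in PCR-confirmed patients. Footnote 1 requires a temperature of 37.3°C or below "within 24 hours (without further increase during observation period"), together with no more than two ARVI symptoms. Footnote 2 gives the source: "Based on a patient diary".

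Under Study design, the diary is for "recording morning and evening axillary body temperature" and disease symptoms, and it also takes "antipyretic dosing (if applicable").

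Symptomatic (Standard) treatment permits, throughout the study, an "antipyretic/non-steroidal anti-inflammatory drug (paracetamol/ibuprofen"). Under "Indications for prescription of antipyretics" it sets thresholds of above 39°C, or above 38°C with listed co-morbidities. It then says: "If antipyretic was taken by the patient on his own (without doctor recommendation) with no indications the patient is not excluded from the study". The next sentence reads: "The patient should record the values of thermometry before taking the drug, its name and dose".

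Secondary endpoint 5 counts antipyretic dosing on days 1 to 3. Statistical Analyses provides intention-to-treat and per-protocol analyses. Its deviation list names prohibited therapy, not the permitted antipyretics.

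**The concern.** Paracetamol or ibuprofen can hold a temperature under 37.3°C while the illness continues. With scheduled readings only morning and evening, a 24-hour window rests on two or three values, and some may be taken under a dose. The plan asks for a pre-dose temperature but does not say whether it enters the endpoint. Take an invented patient with 36.9°C in the morning, 37.8°C before an afternoon dose and 37.0°C in the evening. The window qualifies on scheduled readings and fails on all readings, so two programmers could date the event differently.

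If placebo patients dosed more near the end of fever, their resolution would be dated too early and the treatment difference diluted. The study has about 80% power at its stated minimum detectable effect and little margin. The one antipyretic endpoint stops at day 3, before most patients are expected to resolve, so it would say little about dosing near resolution.

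**Working it through.** **Inputs from the protocol (Evaluation of sample size).** SD 1.38 days; 120 evaluable patients, so 60 per arm; two-sided α = 0.05; power 80%; minimum detectable effect 0.71 day. Drug-arm time is the maximum of N(2.6, 1.77) and N(5, 1.47), independent, approximated by N(5.17, 1.38).

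**Plan's own figure.** The standard error is 1.38 × √(2/60) = 0.252. The minimum detectable effect is (1.960 + 0.842) × 0.252 = 0.706, which agrees with the stated 0.71. Power at 0.71 is Φ(0.71/0.252 − 1.96) = 80.5%. Simulating the maximum gives mean 5.18 and SD 1.36, close to the plan's 5.17 and 1.38.

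**Resolution by day 3.** Drug: Φ((3 − 5.17)/1.38) = 5.8%. Placebo, if 0.71 day slower: Φ((3 − 5.88)/1.38) = 1.8%. Secondary endpoint 5 therefore does largely miss the period of resolution.

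**Dilution from masking (assumed rates).** The documents give no antipyretic use rates and do not say which planning domain is fever. Assume that 10 to 20 percentage points more placebo than drug patients have fever masked, by 0.5 or 1 day. Placebo is made 0.71 day slower on average in three ways: both domains later by 0.71, the shorter only by 2.33, or the longer only by 0.80. The average loss in the maximum per masked patient, in days, is:

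| Fever is | Masked by | Both shifted | Shorter only | Longer only |
|---|---|---|---|---|
| Shorter domain | 0.5 day | 0.063 | 0.223 | 0.034 |
| Shorter domain | 1 day | 0.106 | 0.404 | 0.055 |
| Longer domain | 0.5 day | 0.412 | 0.234 | 0.450 |
| Longer domain | 1 day | 0.793 | 0.425 | 0.878 |

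Shrinkage is the excess fraction times the loss, and power is Φ((0.71 − shrinkage)/0.252 − 1.96).

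- Fever the shorter domain: 0.10 × 0.034 = 0.003 up to 0.20 × 0.404 = 0.081 day; power 80% down to 70%.
- Fever the longer domain: 0.10 × 0.234 = 0.023 up to 0.20 × 0.878 = 0.176 day; power 78% down to 56%.
- Power stays at 75% or more while shrinkage is no greater than 0.046 day.

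Equal masking in both arms gives no shift in the mean difference. Excess masking on drug would bias it the other way.

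**What a dose-free-window analysis would measure.** Afebrile patients who dose for pain would be counted as unresolved. If this is 10 to 20 points more common on placebo and delays them by 1 to 2 days (also assumed), the result moves toward the drug by 0.10 × 1 = 0.10 to 0.20 × 2 = 0.40 day. That is generally larger than the 0.003 to 0.176 day it is meant to reveal.

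**Safeguards already in the text.** The bar on a further increase is not limited to scheduled readings. A dose taken for a stated indication follows a reading above 38°C or 39°C, which breaks the window if that reading counts. The condition on symptoms must hold as well. What remains is mainly repeated off-indication dosing as fever ends, at an unknown rate.

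**The case for a change.** The strongest case for a change is that the rule costs one sentence, settles which readings date the primary event, and removes a choice otherwise made at programming. Secondary endpoints 2 to 4 use the same resolution concept and inherit the ambiguity. The safeguards work fully only if pre-dose readings count, which is the very thing left unsaid. The pre-dose instruction follows the self-medication sentence, so it may not cover every dose.

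Much of this stands as description. It is useful to write down which readings count in the derivation specification before unblinding, and a count of antipyretic use by arm up to resolution would be informative.

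It does not establish a fault in the plan. A sentence saying that all recorded temperatures count either repeats the natural reading of the footnote or is a trade-off. Patients who dose supply extra readings and so have more chances to record fever. If they are mostly on placebo, that lengthens placebo times and favours the drug, so a risk of dilution is exchanged for a possible bias in the other direction. Nor is it certain that the data would support a window-based analysis. The protocol does not say where the pre-dose reading is stored and does not mention dose time. Antipyretic use after day 3 is not wholly unseen either, since concomitant therapy is recorded at Visits 1, 2 and 3 (days 1, 5 and 7).

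**Conclusion.** No change is needed. The document describes itself as a protocol summary, and the missing reading-level rule is a detail that analysts can fill sensibly from the footnote, the diary and the pre-dose instruction. The primary approach, which counts outcomes whatever permitted symptomatic treatment was taken, is sound. Nothing in the documents shows that its result would be wrong.

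The possible loss is 0.003 to 0.18 day of a 0.71-day difference, with power between 80% and 56%. That range rests entirely on an assumed placebo excess of 10 to 20 points and 0.5 to 1 day of masking, and the lowest power needs every assumption at its worst. Masking concentrated on placebo would make the trial conservative; equal masking would leave the mean difference unchanged; an excess on drug would act the other way, and the documents cannot say which applies. A dose-free-window analysis would leave the primary result as it is, and its own possible shift of 0.10 to 0.40 day means it could not attribute a difference to masking. It is an optional descriptive addition.

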Patient will be observed for 14 days (screening, randomization - Day 1, treatment period – 5 days, follow-up – up to 2 days; deferred “phone visit” – Day 14).

During the treatment and follow-up period the patients or investigators will make 3 visits and the fourth “phone visit” will be scheduled additionally: 1) visits by physician/patient - on Days 1, 5 and 7 (Visits 1, 2 and 3) – in a study center or at home; 2) “phone visit” (Visit 4) – on Day 14.

At Visits 2 and 3, the investigator will perform an objective examination, document changes in the symptoms and concomitant medications to check patient diaries. At Visit 3 compliance will be evaluated and laboratory tests will be performed. “Phone visit” is carried out to interview the

patient about his/her condition, presence/absence of secondary bacterial/viral complications and use of antibiotics.

During the study, symptomatic therapy and therapy for their co-morbidities are allowed with the exception of the drugs indicated in the section “Prohibited Concomitant Treatment”.

Inclusion and exclusion criteria

Inclusion criteria

1. Patients of either gender aged 18-70 years.
2. Diagnosis of ARVI based on medical examination: axillary temperature $\geq 38.0^{\circ}\text{C}$ at examination + total general symptoms score ≥ 4 , nasal/throat/chest symptoms score ≥ 2 .
3. The first 24 hours after ARVI onset⁵.
4. Patients giving their consent to use reliable contraception during the study.
5. Signed patient information sheet (informed consent form).

Exclusion criteria

1. Clinical symptoms of severe influenza/ARVI⁶ requiring hospitalization.
2. Suspected pneumonia, bacterial infection (including otitis media, sinusitis, urinary tract infection, meningitis, sepsis, etc.) requiring administration of antibiotics from the first day of illness.
3. Suspected initial manifestations of diseases with symptoms similar to ARVI at onset (other infectious diseases, flu-like syndrome at the onset of systemic connective tissue diseases, and other pathology).
4. Patients requiring antiviral medication prohibited within the study.
5. Medical history of primary and secondary immunodeficiency.
6. Medical history/suspicion of oncology of any localization (except for benign neoplasms).
7. Aggravation or decompensation of chronic diseases affecting a patient's ability to participate in the clinical trial.
8. Malabsorption syndrome, including congenital or acquired lactase or other disaccharidase deficiency, galactosemia.

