⁸ If, considering the lack of some data in primary endpoint variable, the fact of reaching the primary endpoint by the patient can still be determined, the patient will be eligible for PP analysis (e.g. the diary lacks some records but the time of recovery can still be determined).

1.6 statistical hypotheses: null and alternative hypotheses about the superiority of the study drug over placebo using the applied dosing regimen:

$$H_0: M_1 - M_2 = 0$$

$$H_a: M_1 - M_2 \neq 0$$

where M_1 – the mean time to resolution of all symptoms in the study drug group;

M_2 – the mean time to resolution of all symptoms in the placebo group.

Analysis of the expected effect within the fixed sample will be carried out in accordance with the following formulas:

$$n_1 = kn_2$$

$$\varepsilon = \left(\frac{(z_{\alpha/2} + z_{\beta})^2 * (1 + 1/k) * \sigma^2}{n_2} \right)^{\frac{1}{2}}$$

where n_1, n_2 – the sample size of the study drug and the placebo groups respectively;

$\varepsilon = M_1 - M_2$ – the minimum detectable difference in time in study drug and placebo groups;

k – the coefficient of study drug /placebo sample ratio ($k=1$);

σ – the standard deviation;

$z_{\alpha/2}$ – a tabulated two-tailed z-test for α ;

z_{β} – a tabulated one-tailed z-test for β .

1.7 effective sample size will be determined using the formula:

$$N_{PP} = N_T * (1 - C_w),$$

where N_T – the final sample size;

N_{PP} – the value calculated in section 1.6, i.e. the expected number of the patients completing the study per protocol;

C_w – withdrawal coefficient.

2. Assumptions about the expected effects of the clinical study: To evaluate the minimum detectable effect at fixed sample size a priori estimate of population parameters should be performed:

A priori estimates for tested parameter variables in the groups:

Primary endpoint (efficacy criterion):

[figure not shown]
Time to resolution of ARVI symptoms.

Study drug group:

Time to resolution of symptoms was estimated on the basis of the previous studies.

$$T_{tr} = (\langle \max(N(2.6, 1.77), N(5, 1.47)) \rangle)^{9,10}$$

Where $\langle \dots \rangle$ stands for averaging operation, $N(x, s)$ – normally distributed random variable with the mean x and standard deviation s . corresponds to the Gumbel type I distribution¹¹ for power analysis this empirical distribution is approximated by the normal distribution with characteristics $m=5.17$, $\sigma=1.38$.

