Note. Red area is empirical distribution of time to resolution of symptoms in Product group (number of simulation repetitions $N=10^5$). Red curve is approximate parametric distribution for the groups.

Therefore, given fixed sample ($N_{pp}=120$) obtained above for population standard deviation ($sd=1.38$) and levels of errors ($\alpha=0.05$, $\beta=0.2$), the minimum detectable effect in the study will be **0.71 day**. When planning the study withdrawal rate of 50% patients was taken¹² ($C_w=0.5$). In total 240 patients will participate in the study.

Statistical criteria

All the statistical calculations will be performed using two groups of statistical criteria:

- parametric – to obtain effective evaluations for parameters of random values, if the relevant conditions of applicability of methods/models are not violated (e.g. sphericity, normality, proportionality of risks, etc.);
- non-parametric – in any other cases.

Parametric criteria

⁹ Based on the clinical trial “A study to assess the therapeutic efficacy and safety of Anaferon against influenza and other upper respiratory tract infections in adults” [11]. Duration distributions for symptom domains are considered independent. 95% confidence interval is taken for the corresponding standard deviations.

¹⁰ The data resulting in major variance evaluation are used.

¹¹ On the distribution of the maximum of N independent normal random variables: IID and INID cases. SDSSU Multidisciplinary Research Journal Vol. 1 No. 2±2013

¹² This rate is complex: 10% patients will be screening failures or will withdraw for other reasons specified in the relevant protocol section, 44% remaining patient will not have the diagnosis verified by PCR.

The application of parametric criteria will be accompanied by a check of models for applicability (e.g. Kolmogorov-Smirnov test, Shapiro-Wilk test, etc.).

The following parameters and approaches are to be used:

1. To evaluate the differences of continuous variables obtained in one group at two different visits – Student's test for matched samples.
2. To evaluate the temporal dynamics of the compared indicators – analysis of variance (ANOVA) or covariance (ANCOVA) in the modification with repeated measures.
3. In case of multiple comparisons between the groups will apply a variety of corrections for multiplicity (Dunnett, Tukey, Scheffe, Holm adaptive test), etc.

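### Do the primary event ("absence/presence of ARVI symptoms ≤ 2", unit not stated) and the hypotheses (all symptoms resolved) describe two different endpoints?

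*Combined protocol and SAP*

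**What the plan says.** **Event.** In the Endpoints section, footnote 1 defines resolution by two conditions that must both hold: temperature at or below 37.30°C within 24 hours without a later rise, and "absence/presence of ARVI symptoms ≤ 2". Secondary endpoints 2 to 4 use the same term.

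**Hypotheses.** Under Evaluation of sample size, item 1.6 defines M1 as "the mean time to resolution of all symptoms in the study drug group" and M2 as "the mean time to resolution of all symptoms in the placebo group".

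**Planning.** Item 2 of that section names the primary endpoint and takes as its planning variable the larger of two normal variables, one with mean 2.6 and SD 1.77, the other with mean 5 and SD 1.47. This is approximated by a normal distribution with mean 5.17 and SD 1.38. Footnote 9 adds: "Duration distributions for symptom domains are considered independent". The domains are not named. With 120 evaluable patients the section concludes that "the minimum detectable effect in the study will be" 0.71 day.

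**Scales.** Inclusion criterion 2 asks for an axillary temperature of at least 38.0°C and "total general symptoms score ≥ 4 , nasal/throat/chest symptoms score ≥ 2". The diary records "disease symptoms (Symptom Severity Score"), and the Study design section says that severity is rated on a 4-point scale.

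**The concern.** Taken literally, an event that lets symptoms remain is not the disappearance of all symptoms, so the hypotheses seem to name a different quantity from the primary endpoint. The planning variable appears to point the same way: the larger of two domain durations is the time when the last domain ends, and a patient with two symptoms left in one domain could meet footnote 1 before then. In that case the SD of 1.38 and the 0.71-day figure would belong to another event.

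The missing unit adds to the doubt. The 2 could be a number of symptoms, a total score or a grade per symptom, and these give different event times. If the choice were really open, it would be a choice about the primary endpoint made by whoever programs it, and three secondary endpoints would inherit it.

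**Working it through.** **1. Which text defines the event?** Footnote 1 is attached to the primary endpoint and gives criteria that can be programmed from a diary. Item 1.6 only labels the symbols M1 and M2, and its wording enters no number. The word *all* appears only in those two labels. Item 2, which supplies the planning figures, uses the endpoint's own name without it. An analyst would program footnote 1.

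**2. What is the 2?** Where the document means a score it says so: inclusion criterion 2 writes score twice, and footnote 3 speaks of points. Footnote 1 speaks of symptoms being absent or present, which is the language of counting.

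The entry criterion gives a further check. Grades 0 to 3 are assumed, in line with the 4-point scale and footnote 3.

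- A general score of at least 4 needs at least 2 symptoms, since one symptom gives at most 3. A nasal/throat/chest score of at least 2 needs at least 1 symptom.
- The minimum at entry is therefore 2 + 1 = 3 symptoms and 4 + 2 = 6 points.
- As a count (3 > 2) or a total score (6 > 2), the symptom condition is never met at entry.
- As a grade per symptom, it is already met at entry by a patient with general grades 2 and 2 and nasal grade 2. A recovery rule that such a patient satisfies on day 1 is an unlikely intention, which counts against this reading.
- Under every reading the full event is impossible at entry, because entry needs at least 38.0°C and the event needs at most 37.3°C.

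**3. Does the planning figure reproduce?** Inputs from Evaluation of sample size: two-sided α = 0.05, power 80%, SD 1.38, and 120 evaluable patients at 1:1, hence 60 per arm.

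- MDE = (z₀.₉₇₅ + z₀.₈₀) × SD × √(2/n) = (1.960 + 0.842) × 1.38 × √(2/60) = 0.706 day (stated: 0.71).
- Enrolment = 120 / (1 − 0.5) = 240 (stated: 240).
- Simulating the larger of N(2.6, 1.77) and N(5, 1.47) gives mean 5.18 and SD 1.36 (stated: 5.17 and 1.38).

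**4. Does a maximum imply that all symptoms have ended?** No. Footnote 1 needs temperature *and* symptoms to settle, and the time at which two conditions both hold is roughly the larger of the two component times. Footnote 3 lists body temperature among the ARVI symptoms, so the two unnamed domains could be temperature and the other symptoms. The documents do not say whether either duration ran to complete absence. The planning formula fits footnote 1 as well as it fits an all-symptoms event.

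**5. What if the SD differed?** Every SD below except 1.38 is an assumption. The values 1.47 and 1.77 are the plan's single-domain SDs, and nothing ties them to the footnote 1 event.

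| SD | MDE, 60 per arm (days) | Power at 0.71 day |
|---|---|---|
| 1.20 | 0.61 | 90% |
| 1.38 | 0.71 | 80% |
| 1.47 | 0.75 | 75% |
| 1.77 | 0.91 | 59% |

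The effect can go either way. Footnote 10 says that the data giving the larger variance were used, so the planning leaned towards caution.

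**The case for a change.** The strongest case for acting is that the mismatch between footnote 1 and item 1.6 is literal under any unit, and that a primary endpoint should leave nothing to choose. Count and total score are both workable, and they differ: one remaining symptom at grade 3 meets a count of at most 2 but not a total of at most 2. Under the count reading, two general symptoms graded 2 and 2 still reach the general-symptom threshold for entry. And no sentence confirms that the planning durations were counted to the footnote 1 event.

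The literal mismatch stands, and so does the missing unit. The rest carries less weight. That a patient can be counted as recovered with two marked symptoms left bears on how lenient the threshold is, and the concern does not dispute the threshold; fever must also have gone. Total score is possible, but the document's own usage favours a count. That the planning durations are not shown to match footnote 1 is true, but it does not show that they fail to match. If the observed spread turned out larger than planned, the Interim analysis section already allows a blinded look at population parameters with an increase in sample size. The document also describes itself as a protocol summary, so the absence of a symptom list here does not show that none exists.

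**Conclusion.** No change to the plan follows. The wording in item 1.6 is a slip in a label, and the unit of the 2 is a detail that an analyst fills sensibly by counting symptoms as footnote 1 is phrased. Correcting the label would alter no result: the 0.71-day effect and the total of 240 reproduce from the stated inputs and do not depend on it. No bias is claimed, since one rule would apply to both blinded arms. No size or direction of a power effect can be given, because the documents do not state the SD of the footnote 1 event.

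This conclusion assumes that the 2 is read as a number of symptoms, that the reading is settled before unblinding, and that it is used alike for the primary endpoint and secondary endpoints 2 to 4. A source showing that the planning durations ran to complete absence of symptoms would reopen the question of the SD, but not that of the endpoint.
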